3.1.1 Stage A1

The aim is to find the M6620 treatment schedule when combined with radiotherapy that is associated with no more than 25% dose limiting toxicity rate on the basis that palliative oesophageal radiotherapy is associated with approximately 15-20% grade 3/4 toxicity. Six treatment schedules are proposed. Each schedule comprises a specific combination of dose and dosing frequency. There are two possible M6620 doses and three dosing frequencies (see section 4.1.1). The radiation dose remains consistent across all treatment schedules. For the prior estimates of DLT at each treatment schedule, see the skeleton in Table 1.

The treatment involves 3 weeks of daily radiotherapy and M6620 at a pre-determined frequency dependent on the treatment schedule allocated to the individual patient. The follow-up of a further 6 weeks provides a DLT observation window of a total of 9 weeks. An initial cohort of three patients will receive the starting schedule (lowest dosing frequency) at the starting dose, 140mg/m². The fourth patient will not be recruited until all three patients have been followed for the minimum of 9 weeks from the start of radiotherapy or the occurrence of a DLT.

Subsequently, all eligible patients will be continuously recruited and the TiTE-CRM will be used to assign their treatment schedule. To ensure enough information is accumulated to inform the assignment of the treatment schedule to the subsequent patient, recruitment will be managed through allocation of treatment slots (see Protocol section 4.4 for further details).

Stage A1 stopping rules

A phase I dose escalation safety study combining the ATR inhibitor VX-970 with chemoradiotherapy in oesophageal cancer using time to event continual reassessment method (funded by CRUK and Merck)
EudraCT Number: 2015-003965-27

Stage A1 will pause for safety if, at any point in the trial, there is sufficient evidence to suggest that schedule 1 is too toxic. More specifically, we will consider schedule 1 to be too toxic if, given all the available data, there is a high probability that the DLT rate is greater than the target toxicity level of 0.25. If all 3 patients in the first cohort have DLTs then schedule 1 is too toxic and the trial will be re-started. At this point, three extra schedules will be introduced at 90mg/m² and varying dosing frequencies, namely (schedule -3, -2 and -1). Once the trial is restarted, the lowest schedule, schedule -3, will be explored first. There will then be 9 treatment schedules to explore (the original 6 plus the 3 dosing frequencies at the lower dose). If the first 3 patients recruited to schedule -3 experience DLTs then the trial will stop. If schedule 1 is found to be too toxic later in the trial when more than 3 patients have been recruited, a SRC meeting will be convened to decide whether the trial should be restarted using the lower dose of 90mg/m².

Stage A1 will stop for success when either a total of 10 patients have been assigned to a particular treatment schedule or 20 patients have been recruited, whichever occurs first. When 10 patients in Stage A1 have been assigned to a particular treatment schedule, recruitment will be paused until there are no more than three patients without full follow-up (either DLT or 6 weeks after the end of treatment), i.e. until there is full follow-up information on at least seven patients. If the MTD changes, recruitment may start again.

Based on simulations and assuming a patient will be recruited every 8 weeks, the average number of patients required for Stage A1 is 18, which we aim to recruit in 24 months.

3.1.2 Stage A2

The aim is to find the M6620 treatment schedule when combined with palliative combination chemotherapy (Cisplatin and Capecitabine) that is associated with no more than a 30% dose limiting toxicity rate. Four treatment schedules are proposed. Each schedule comprises a specific combination of dose and dosing frequency. There are two possible M6620 doses and two dosing frequencies (see section 4.2.1). Chemotherapy dose remains consistent across all treatment schedules. For the prior estimates of DLT at each treatment schedule see the skeleton in Table 1.

The treatment involves six cycles of chemotherapy with three weekly Cisplatin and Capecitabine and M6620 at a pre-determined frequency dependent on the treatment schedule allocated to the individual patient. The follow-up of a further 8 weeks provides a total observation window of 26 weeks. DLT assessments will be carried out during the first 4 weeks of treatment. The MTD will be determined during this period using the TiTE-CRM. An initial cohort of three patients will receive the starting schedule (lowest dosing frequency) at the starting dose. The fourth patient will not be recruited until all three patients have been followed for a minimum of 4 weeks from the start of chemotherapy or until the occurrence of a DLT.

From the fourth patient, all eligible patients will be continuously recruited and the TiTE-CRM will be used to assign their treatment schedule. To ensure enough information is accumulated to inform the assignment of the treatment schedule to the subsequent patient, recruitment will be managed by allocating treatment slots (see Protocol section 4.4 for further details).

Stage A2 stopping rules

Stage A2 will stop for safety if, at any point in the trial, there is sufficient evidence to suggest that schedule 1 is too toxic. More specifically, we will consider schedule 1 to be too toxic if, given all the available data, there is a high probability that the DLT rate is greater than the target toxicity level of 0.3. If the first three patients recruited to Stage A2 have DLTs at treatment schedule 1, then the starting schedule (treatment schedule 1) will be deemed too toxic and the trial will stop.

The trial will stop for success when either six patients have been assigned to the fourth treatment schedule (140 mg/m² of M6620 twice weekly) or 20 patients in total have been recruited, whichever occurs first. When six patients in Stage A2 have been assigned to the fourth treatment schedule, recruitment to Stage A2 will be paused until there is full follow-up information on at least five patients. If the MTD has changed, recruitment to Stage A2 may start again.

Based on simulations and assuming a patient will be recruited every 3 weeks, the average number of patients required for Stage A2 is 16, which we aim to recruit in 12 months.

3.1.3 Stage B

The aim is to find the M6620 treatment schedule when combined with chemoradiotherapy that is associated with no more than 45% dose limiting toxicity rate on the basis that conventional oesophageal chemoradiation causes a grade 3 and 4 toxic event rate of 28% haematological toxicity and 63% non-haematological toxicity, of which 34% is gastrointestinal, as reported in the standard arm of the SCOPE1 study. Comparable toxicity rates were described in the standard arm of the PRODIGE5/ACCORD17 study: grade 3 and 4 neutropenia 29% and grade 3 and 4 dysphagia and oesophagitis 33%. A maximum of 25 patients will be recruited to Stage B.

There are three proposed M6620 treatment schedules (same dose but increasing dosing frequencies, section 4.3.1) to be explored during Stage B. M6620 treatment schedule assignment will occur prior to the start of chemoradiotherapy 6 weeks after a patient is recruited. This will maximise the accumulation of information on each patient before deciding on the treatment schedule for the subsequent patient.

The dose of M6620 (Berzosertib) in Stage B will be 140mg/m², allocation will start on schedule 1, which is the middle of the 3 schedules. Recruitment will be continuous; however, escalation will not occur until at least one patient full DLT window of 24 weeks is complete. At this point escalation to schedule 2 will be possible if it is estimated to be safe, and dose decisions thereafter will be made once each new patient is recruited and confirmed (if there is reason to think their allocation may have changed) when they have been treated for 6 weeks (the induction period which is the same for all schedules). De-escalation to schedule -1 is possible at any point in the trial. Although recruitment will be continuous, the TMG retain the option to pause recruitment should they decide more follow-up data is needed before continuing. This may be, for example, to prevent too many patients being treated with a sub-optimal, or too toxic, schedule. No more than 7 patients will be treated on schedule 1 before there is full follow-up data on at least one patient. The starting dose of M6620 in Stage B will be 140mg/m² if both A1 and A2 recommend 140mg/m² otherwise it will be 90mg/m².

We will recommend starting stage B:

- If 10 patients have been recruited to A1 and it has not restarted at the lower dose
- If 10 patients have been assigned to at least schedule 3 in A2 (i.e. are on any of the schedules with a dose of 140mg/m²) or the stopping rule is satisfied (6 treated on schedule 4)

If one of the above starting rules are satisfied then an SRC meeting will be convened to review the data and may recommend starting stage B.

Stage B stopping rules

Stage B will stop for safety if, at any point in the trial, there is sufficient evidence to suggest that schedule -1 is too toxic. More specifically, we will consider schedule -1 to be too toxic if, given all the available data, there is a high probability that the DLT rate is greater than the target toxicity level of 0.45. There will be no early stopping rules for success. We expect to recruit a minimum of 15 patients.

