2 TRIAL DESIGN

This will be a single arm, open-label, phase I dose escalation trial using the Time-To-Event Continual Reassessment Method (TiTE-CRM) to find the optimal treatment schedule. The TiTE-CRM method uses critical toxicity summaries of accumulated patient data from all participants treated with at least one dose of the IMP within the corresponding trial stage and for whom up-to-date data has been provided (trial unit will endeavour to ensure contemporaneous data is received for all participants) and it is not necessary for a patient to complete the full observation period before consenting the next patient. This results in a better estimation of the MTD and shorter study duration respectively and is particularly useful in trials involving radiotherapy where the toxicity follow-up phase is longer.

The trial design ensures no treatment schedule skipping and the treatment schedule assigned will be that estimated to be closest to but not above the MTD. However, if the lowest schedule is estimated to be above the MTD we will keep assigning the lowest schedule until we are certain it is too toxic, at which point the trial may start again using a lower dose of drug. When escalating, the treatment schedule cannot skip an untried dose but there will be no restriction on treatment schedule de-escalation. Each escalation decision will be made by the TMG based on the recommendation from the TiTE-CRM model and the accumulated experience of the

recommended schedule. If the TMG is unable to reach a decision or a stopping rule has been met the Safety Review Committee (SRC) will meet.

The trial consists of three stages A1, A2 and B which are described in the following sections. Stages A1 and A2 will run concurrently and will inform the starting dose of M6620 (Berzosertib) for Stage B.

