2.3 Stage B

The aim is to find the M6620 (Berzosertib) treatment schedule when combined with chemoradiotherapy that is associated with no more than 45% dose limiting toxicity rate on the basis that conventional oesophageal chemoradiation causes a grade 3 and 4 toxic event rate of 28% haematological toxicity and 63% non-haematological toxicity, of which 34% is gastrointestinal, as reported in the standard arm of the SCOPE1 study. Comparable toxicity rates were described in the standard arm of the PRODIGE5/ACCORD17 study: grade 3 and 4 neutropenia 29% and grade 3 and 4 dysphagia and oesophagitis 33% (13). A maximum of 25 patients will be recruited to Stage B.

There are three proposed M6620 (Berzosertib) treatment schedules (same dose but increasing dosing frequencies) to be explored during Stage B. Before each patient enters Stage B, a TMG will be held to confirm recruitment. If permitted to enrol in the study, the patient will also be assigned a provisional treatment schedule based on the TiTE-CRM's recommendation. If necessary, a confirmation meeting for the M6620 (Berzosertib) treatment schedule assignment will occur prior to the start of chemoradiotherapy 6 weeks after a patient is recruited. This will maximise the accumulation of information on each patient before deciding on the treatment schedule for the subsequent patient.

The dose of M6620 (Berzosertib) in Stage B will be 140mg/m², allocation will start on schedule 1, which is the middle of the 3 schedules. Recruitment will be continuous; however, escalation will not occur until at least one patient full DLT window of 24 weeks is complete. At this point escalation to schedule 2 will be possible if it is estimated to be safe, and dose decisions thereafter will be made once each new patient is recruited and confirmed (if there is reason to think their allocation may have changed) when they have been treated for 6 weeks (the induction period which is the same for all schedules). De-escalation to schedule -1 is possible at any point in the trial. Although recruitment will be continuous, the TMG retain the option to pause recruitment should they decide more follow-up data is needed before continuing. This may be, for example, to prevent too many patients being treated with a sub-optimal, or too toxic, schedule. No more than 7 patients will be treated on schedule 1 before there is full follow-up data on at least one patient.

We will recommend starting stage B:

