8.3 Stage B Treatment

The dose administered in stage B will be 140mg/m² (see section 2.3) and will remain constant whilst three dosing schedules are explored (see table 8.3). The chemotherapy and radiation doses and fractionation schedules will remain unchanged across dosing schedules.

The 11 weeks of treatment consists of 6 weeks of induction chemotherapy (Capecitabine and Cisplatin) with M6620 (Berzosertib) followed by 5 weeks of concomitant chemoradiotherapy (Capecitabine, Cisplatin and radiotherapy) with M6620 (Berzosertib). All patients will receive M6620 (Berzosertib) with induction chemotherapy on Cycle 1 Day 2 and Cycle 2 Day 2. In the last week of chemotherapy patients will be assigned to a M6620 (Berzosertib) treatment schedule to be administered during chemoradiotherapy (see table 8.3 below). Radiotherapy must start on a Monday.

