8.3.1 M6620 (Berzosertib) Treatment dose and schedule – Stage B

The dose of M6620 (Berzosertib) in Stage B will be 140mg/m², allocation will start on schedule 1.

Table 8.3

Dose Escalation Schedule		
Treatment Schedule	M6620 (Berzosertib) administration during induction chemotherapy	M6620 (Berzosertib) administration during Chemoradiotherapy
-1	Cycle 1 day 2, Cycle 2 day 2	Days 2, 9, 16, 23, 30
1*	As above	Days 2, 5 , 9, 16, 23, 26 , 30
2	As above	Days 2, 5, 9, 12, 16, 19 , 23, 26, 30, 33

*Starting schedule. Reduced frequency schedule (-1) will only be explored if schedule 1 is too toxic.

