3. STUDY METHODS

3.1 Trial Design/framework

This will be a single arm, open-label, phase I dose escalation trial using the Time-To-Event Continual Reassessment Method (TiTE-CRM) to find the optimal treatment schedule. The trial consists of three stages A1, A2 and B. Stages A1 and A2 will run concurrently and will inform the starting dose of M6620 for Stage B.

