4.3 Stage B Treatment

The dose administered in stage B will be 140mg/m² and will remain constant whilst three dosing schedules are explored. The chemotherapy and radiation doses and fractionation schedules will remain unchanged across dosing schedules.

The 11 weeks of treatment consists of 6 weeks of induction chemotherapy (Capecitabine and Cisplatin) with M6620 (Berzosertib) followed by 5 weeks of concomitant chemoradiotherapy (Capecitabine, Cisplatin and radiotherapy) with M6620 (Berzosertib). All patients will receive M6620 (Berzosertib) with induction chemotherapy on Cycle 1 Day 2 and Cycle 2 Day 2. In the last week of chemotherapy patients will be assigned to a M6620 (Berzosertib) treatment schedule to be administered during chemoradiotherapy. Radiotherapy must start on a Monday.

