4.3.1 M6620 Treatment Dose and Schedule – Stage B

The dose of M6620 in Stage B will be confirmed prior to recruitment to stage B and the starting schedule will be treatment schedule 1.

Table 4: Stage B - Dose Escalation Schedule

Dose Escalation Schedule		
Treatment Schedule	M6620 administration during induction chemotherapy	M6620 administration during Chemoradiotherapy
-1	Cycle 1 day 2, Cycle 2 day 2	Days 9, 16, 23, 30
1	As above	Days 2, 5, 9, 16, 23, 26, 30
2	As above	Days 2, 5, 9, 12, 16, 19, 23, 26, 30, 33

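### The SAP gives the Stage B M6620 dose both as a fixed 140 mg/m² and as a conditional 140 or 90 mg/m², and its schedule -1 days differ from the Protocol's

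*SAP*

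**What the plan says.** **Dose.** SAP 3.1.3 states 140 mg/m² for Stage B and adds, at the end of the same paragraph, that the starting dose is 140 only "if both A1 and A2 recommend" 140, and otherwise 90. SAP 4.3 gives 140, which "will remain constant whilst three dosing schedules are explored". SAP 4.3.1 reads: "The dose of M6620 in Stage B will be confirmed prior to recruitment to stage B". In the Protocol, section 2.3 sets 140 and continues "allocation will start on schedule 1, which is the middle of the 3 schedules"; sections 8.3 and 8.3.1 also give 140, with no condition. Protocol section 2 says that Stages A1 and A2 "will inform the starting dose of M6620 (Berzosertib) for Stage B", and SAP 3.1 says the same.

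**Schedule -1 days in chemoradiotherapy.** Protocol Table 8.3 has "Days 2, 9, 16, 23, 30". SAP Table 4 has days 9, 16, 23 and 30. Schedules 1 and 2 have identical days in the two tables.

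**Footnotes.** Footnotes 5 to 8 of the Protocol's Stage B schedule of events apply to schedules 3 to 6, in shrinking subsets. Table 8.3 contains only -1, 1 and 2, and Protocol 2.3 confirms that there are three schedules.

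**Status of the SAP text.** The note in SAP 1.2 says that references to the Stage B dose allocation methods were taken out of this version, and promises an update with the Stage B analysis methods before Stage B recruits.

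**The concern.** These are dosing statements, and two people working from different sections could reach different answers. The conditional sentence contradicts the sentence before it in the SAP and has no counterpart in the Protocol. The schedule -1 mismatch concerns the level on which both documents judge whether Stage B must stop for toxicity (Protocol 2.3.1; SAP 3.1.3, Stage B stopping rules). That level needs one defined exposure. It also changes what the week 7 biopsy measures. The Stage B tertiary objective (Protocol 3.2) looks for ATR inhibition in M6620-treated tissue, and the two day lists place the last M6620 dose at very different distances from the biopsy.

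**Working it through.** The documents state no cumulative Stage B dose, so there is no figure of theirs to reproduce. The check is a comparison of passages plus simple arithmetic.

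**Can the conditional branch be reached?** Protocol 2.3 and SAP 3.1.3 list two start rules: ten patients recruited to A1 without a restart at the lower dose; or, in A2, ten patients on schedule 3 or above or the A2 stopping rule met. Both documents then say that satisfying one rule is enough to convene the SRC, which may recommend starting. Stage B could therefore open on the A1 rule before A2 has recommended 140. In that case the SAP condition gives 90 and the Protocol gives 140.

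**Planned totals.** Infusions = 2 induction doses (cycle 1 day 2 and cycle 2 day 2, all patients) + chemoradiotherapy doses. Total = infusions × dose per m².

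| Schedule | Source of days | Infusions | Dose (mg/m²) | Total (mg/m²) |
|---|---|---|---|---|
| 1 (start) | both documents | 2 + 7 = 9 | 140 | 9 × 140 = 1260 |
| 1 (start) | both documents | 2 + 7 = 9 | 90 | 9 × 90 = 810 |
| -1 | Protocol Table 8.3 | 2 + 5 = 7 | 140 | 7 × 140 = 980 |
| -1 | SAP Table 4 | 2 + 4 = 6 | 140 | 6 × 140 = 840 |

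Relative differences: 1 - 810/1260 = 0.357 for the dose conflict on schedule 1; 1 - 840/980 = 0.143 for the day-list conflict on schedule -1.

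**Week 7 biopsy on schedule -1, assuming no delays.**
- Week 7 day 1 is trial day 6 × 7 + 1 = 43, so week 7 day 3 is day 45.
- Protocol list: the last M6620 dose is chemoradiotherapy day 2, trial day 44. Gap 45 - 44 = 1 day.
- SAP list: the last M6620 dose is cycle 2 day 2, trial day 21 + 2 = 23. Gap 45 - 23 = 22 days.

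**Footnotes.** The schedules named in footnotes 5 to 8 are 3, 4, 5 and 6. None of them is among -1, 1 and 2. The grid to which the footnotes attach is not visible in the available text, so the affected entries cannot be identified. For the same reason footnote 4, which excepts schedule 1, cannot be checked.

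**The case against.** The best defence is that the Stage B text in this SAP is provisional. SAP 1.2 promises an update before Stage B opens, and SAP Table 1 leaves the Stage B column empty, so no Stage B model input in this version depends on Table 4. The Protocol's explicit dose statements agree with one another, and its amendment history (Appendix E) records a Stage B redesign that included confirming the dose. The conditional sentence is therefore plausibly a leftover. Schedule -1 is also a contingency, used only if schedule 1 proves too toxic. All of this stands and lowers the practical risk. It does not remove the conflict: the note in SAP 1.2 names neither the dose rule nor the day list, and a SAP update cannot correct Protocol footnotes.

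The day-list evidence has limits. The Protocol 8.3.4 dosing grid is broken in the text extracted from the PDF, so the Protocol side rests on Table 8.3 alone. A lost entry for day 2 in SAP Table 4 cannot be fully excluded, although the row reads cleanly.

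A reader might infer that, under the SAP list, the week 7 biopsy breaks the Protocol's timing rule or must miss its fraction window. The documents do not support that. Protocol 7.2.1 applies the 24-hour interval only where M6620 has been given. The missed-window argument would also require radiotherapy at about the same clock time on chemoradiotherapy days 9 and 10, and no clock time is fixed. A reader might also combine the shorter day list with the lower dose into one larger discrepancy. They are two separate conflicts, and the combined figure measures the size of neither.

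**Conclusion.** The contradictions stand in the current text and should be resolved before Stage B opens.

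- **Dose:** the conflict lies within the SAP, and between the SAP and the Protocol; the 140-or-90 rule appears in SAP 3.1.3 only. On starting schedule 1 the lower reading is 36% below the higher. The sentences about A1 and A2 informing the dose, and about confirming it later, fit either reading and settle nothing.
- **Schedule -1:** the two tables differ by one infusion, 14% of the planned total at 140 mg/m². This is subject to checking the source files. The 22-day gap before the biopsy would weaken the ATR-inhibition readout without breaching a timing rule, and assumes an uninterrupted schedule.
- **Footnotes:** a minor error. No specific consequence is claimed, because Protocol 5.5.1 ties the main assessments to M6620 administration whatever the schedule number.

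Nothing here shows that any patient has been or will be dosed wrongly, or that any model calculation is affected. Which dose and which days apply is for the sponsor and the SRC.

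**What to change.** Before Stage B opens:

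1. Reconcile SAP 3.1.3, 4.3 and 4.3.1 with each other and with Protocol 2.3, 8.3 and 8.3.1, so that one dose rule appears throughout. Align the sentences in Protocol section 2 and SAP 3.1 about A1 and A2 informing the starting dose with that rule.
2. Check the source files, then reconcile the schedule -1 days across Protocol Table 8.3, the Protocol 8.3.4 grid and SAP Table 4. Read the week 7 biopsy timing in Protocol 7.2.1 against the agreed list.
3. Name these SAP items explicitly among those to be closed in the update promised in SAP 1.2.
4. At the next Protocol amendment, re-key or delete footnotes 5 to 8 of the Stage B schedule of events, and check footnote 4.

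Cost: wording changes in a SAP update that is already planned. The footnotes, and any Protocol dose or day text that changes, need a Protocol amendment. A change of dose or days may count as substantial, and would then need approvals in place before use (Protocol 22.4). No patients or visits are added.
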